[U- $^{13}\text{C}_3$] glycerol 50 mg/kg (obtained from Cambridge Isotopes, Andover, MA) will be given to participants to drink. It is non-radioactive and non-toxic. There is no known risk to drinking glycerol. Ingestion of this item is similar to drinking a commercial sugar sweetened beverage. If a participant cannot tolerate the drink initially, they will be given a second attempt at ingestion. If after two attempts they cannot ingest the entire item, they will be removed from the study and a replacement participant will be recruited.

Aim 2 will be an extension of Aim 1 in which all participants from Aim 1 will receive empagliflozin study drug or placebo for 12 weeks and then return for repeat testing. Participants stratified by VAT (high vs. low) will be randomized to either treatment or placebo using a random number generator (0-100, <http://www.random.org>) followed by the creation of numbered envelopes; \leq median will be assigned to treatment and $>$ median will be assigned to placebo. The minimum approved dose of empagliflozin (10 mg tablet daily by mouth taken in the morning with or without food) will be used in Aim 2 of this study; this dose was chosen to minimize the chances of adverse events (specifically hypoglycemia, dehydration, and urinary tract infections) while still maintaining efficacy in clinical trials and preliminary data. We expect that this dose will be well tolerated, with the most common side effects being urinary tract infection or yeast infection (in women).

Outcome variables:

[U-¹³C₃] glycerol enrichment in plasma blood glucose over time will be measured by nuclear magnetic resonance spectroscopy.

4. Study Procedures:

Study procedures are outlined below. Study procedures will be performed at baseline and then repeated after 3 months of study drug administration. There will also be two (2) interval visits during which study participants will meet with the study coordinator to review study drug adherence, obtain the next month's supply of study drug, and perform surveillance for any adverse effects.

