Study drug will be either empagliflozin (10 mg once daily by mouth) or matching placebo (once daily by mouth). Both active drug and placebo will be obtained from the manufacturer (Boehringer-Ingelheim) and will be administered by study staff (blinded to treatment allocation) in oral tablet form. Participants will be randomized to either active drug or placebo using a random number generator (0-100, <http://www.random.org>); ≤median will be assigned to empagliflozin and >median will be assigned to placebo.

Study Procedures Visits 1 and 4

1. Arrive at AIRC
 2. Review study procedures
 3. Sign written informed consent
 4. Urine pregnancy test to verify non-pregnant status (female only)
 5. Measurement of height, weight, body composition, heart rate, blood pressure, and temperature.
 6. Possible neck-to-knee MRI
 7. IV insertion by AIRC nurse for blood draws
 8. Baseline blood draw.
 9. Ingestion of [U-¹³C₃] glycerol (50 mg/kg body weight)
 10. Blood draws: +30, +60, +90, +120, +150, +180 min. Each blood draw will be 41 ml for a total of 312 ml (includes 25 ml waste)
 11. IV discontinued
 12. Lunch and discharge from AIRC. Study participation completed.
- Each study visit 1 and 4 will be approximately 5 hours.

Study Procedures Visits 2 and 3

1. Arrive at AIRC
2. Return study drug pill bottle and review study drug adherence
3. Assess for any interval adverse effects and document as necessary
4. Dispense study drug to be used in the next study visit interval (1 month)
5. Discharge from the AIRC.

Study participants do not need to be fasting for Visits 2 or 3 and no blood will be drawn at these interval visits. They are for study drug adherence/monitoring and drug dispensing only. Each study visit 2 and 3 will be approximately 30-60 minutes.

After the ingestion of the glycerol and during the blood draws, volunteers will be made comfortable in the AIRC procedure room. Conditions that would result in the subject exiting the study prior to the expected completion date include withdrawal of informed consent, intolerance of the glycerol drink, intolerance of study procedures (IV insertion, blood draws), or meeting exclusion criteria that were not previously known through telephone screening. Research subjects will not be responsible for any costs of the study.

5. Sub-Study Procedures: N/A

6. Criteria for Inclusion of Subjects:

- Obese, defined as BMI ≥ 30 kg/m², at both time of abdominal fat imaging and at study entry.
- Ages 30-65

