A partial waiver of HIPPA authorization for screening purposes will be requested. This is a waiver used only for collection of initial screening data to determine eligibility and/or recruit potential research subjects. Authorization by the subject will be obtained at the time of consent. This is justified because it is not practical to obtain a signed HIPPA Authorization form prior to review of the records of potential participants because review of records is required to screen for a participant's eligibility for study participation. Over 3000 HIPPA Authorization forms (all participants in phase 3 of the Dallas Heart Study) would need to be completed prior to screening of records to determine the eligibility of study participants if records cannot be reviewed for eligibility purposes beforehand. This is not practical and the study could not be effectively conducted in this manner. Inclusion and exclusion criteria could not be determined without access to the PHI. This would also not be possible with the use of de-identified information.

10. Potential Risks:

- *Adverse Reaction to Empagliflozin*

Known adverse effects of empagliflozin include hypoglycemia (0.4%), dehydration (0.3%), impaired renal function (change in eGFR -1.0 mL/min/1.73 m² compared placebo), and an increased risk of urinary tract infection (9.3%) or vaginal yeast infection (5.4%). The most common adverse reactions associated with empagliflozin were urinary tract infections and vaginal yeast infections.

- *Risks of IV Insertion and Blood Drawing*

Participants may experience a small amount of pain in the arm when the needle is inserted into the vein. Risks associated with drawing blood from the arm include minimal discomfort and/or bruising. Infection, excess bleeding, clotting, and/or fainting also are possible, although unlikely. Participants will have less than 1½ cups of blood collected because they are in this research study.

- *¹³C Labeled Glycerol*

Labeled glycerol is non-radioactive and non-toxic and there is no known risk to drinking labeled glycerol. The glycerol will taste sweet and will be mixed with a glass of drinking water.

- *MRI*

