0855			Collect 40ml blood sample in purple top and 1ml blood sample for blood sugar. YSI Result: _____ / _____ mg/dl
0915 -0930			Prepare for subjects receiving [U-13C3]glycerol in ½ cup filtered water: _____ kg x 0.05 gm/kg x 1 ml/1.302 gm = _____ ml Lot#: _____ Exp: n/a
0930			Have subject drink Glycerol. Follow with 1 cup filtered water to rinse bottle.
1000 +30			Collect 1ml for blood sugar and 40ml blood sample in purple top tubes. YSI Result: _____ / _____ mg/dl
1030 +60			Collect 1ml for blood sugar and 40ml blood sample in purple top tubes. YSI Result: _____ / _____ mg/dl
1100 +90			Collect 1ml for blood sugar and 40ml blood sample in purple top tubes. YSI Result: _____ / _____ mg/dl
1130 +120			Collect 1ml for blood sugar and 40ml blood sample in purple top tubes. YSI Result: _____ / _____ mg/dl
1200 +150			Collect 1ml for blood sugar and 40ml blood sample in purple top tubes. YSI Result: _____ / _____ mg/dl

Advanced Imaging Research Center

eIRB File #: 012015-064

Visceral Adiposity and Diabetes: Translating Form to Function Using Imaging

Subject Name:		Visit Date:	
Scheduled Time	Actual Time	Initials	AIRC Outpatient Procedure
1230 +180			Collect 1ml for blood sugar and 40ml blood sample in purple top tubes. YSI Result: _____ / _____ mg/dl
			Discontinue peripheral IV line after last blood sample obtained.
			Obtain vital signs. BP: _____ / _____ P: _____ T: _____ °F R: _____
			Provide lunch.
			Perform MRI scan if indicated
			On Study Day 1 Provide Emagliflozin/Placebo and Instructions.
			Discharge subject from AIRC.

Advanced Imaging Research Center eIRB File #: 012015-064 Visceral Adiposity and Diabetes: Translating Form to Function Using Imaging				
Study Time	Plasma (Pre) (40ml)	Glucose (1ml)	NMR (40ml)	Comments
				Arrive @ AIRC Start IV x 1
-60 (Pre)	X	X		
0				Glycerol consumed
+15		X	X	
+30		X	X	
+60		X	X	
+90		X	X	
+120		X	X	
+150		X	X	
+180		X	X	
				D/C IV & provide lunch
Tubes	10ml purple top tube x 1	1ml microfuge tube	10ml purple top tube x 4	
Processing	On ice → spin → plasma in small vial → REFRIGERATOR for [name]/[name]	IMMEDIATELY spin → run → record result → plasma in cryo vial for [name]/[name]	On ice → spin → plasma divide into 3 10ml plastic vials → REFRIGERATOR for [name]/[name]	

Glycerol Study Procedure Grid

VISIT 2 and VISIT 3 STUDY MEDICATION COMPLIANCE FORM

DID SUBJECT RETURN UNUSED AND/OR EMPTY MEDICATION CONTAINERS?

YES NO

If no, comment below:

Date of Last Dose Dispensed: ____/____/____
Day Mon Year

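### The risk section's limit of under 1½ cups of blood holds for one sampling visit only; a participant who completes Visits 1 and 4 gives 624 ml, about 1.7 to 1.8 times that limit

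*Combined protocol and SAP*

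**What the plan says.** Section 10 (Potential Risks, IV insertion and blood drawing) makes one statement about volume: "Participants will have less than 1½ cups of blood collected because they are in this research study".

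Section 4 sets out the sampling under the heading "Study Procedures Visits 1 and 4". It lists one baseline draw, then "Blood draws: +30, +60, +90, +120, +150, +180 min", followed by the volumes: "Each blood draw will be 41 ml for a total of 312 ml (includes 25 ml waste", closing bracket omitted. The opening of Section 4 confirms the repetition: "Study procedures will be performed at baseline and then repeated after 3 months of study drug administration". Section 3 (Intervention) has every Aim 1 participant return for repeat testing after 12 weeks of drug or placebo. Section 4 also says that no blood is taken at Visits 2 and 3.

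Two working documents at the end of the protocol repeat the schedule:

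- **Glycerol Study Protocol Flowsheet.** The 0855 pre-dose entry reads "Collect 40ml blood sample in purple top and 1ml blood sample for blood sugar". The post-dose entries run from +30 to +180 min in steps of 30 minutes, as in Section 4.
- **Glycerol Study Procedure Grid.** The pre-dose column is headed "Plasma (Pre) (40ml" (closing bracket omitted), but the tube row for the same column gives "10ml purple top tube x 1". The grid also has a +15 min row, marked for both glucose and NMR, that appears in neither Section 4 nor the flowsheet.

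**The concern.** The risk sentence describes what a participant gives by taking part, so it should cover the whole study. The 312 ml in Section 4 appears to be the amount for one visit, and that visit is done twice. If so, the risk section understates the blood taken from every participant who completes the study.

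What is at stake is the accuracy of a safety statement, not an estimate of treatment effect. The protocol undertakes in Section 11 to inform subjects fully about study requirements, and this is the only blood-volume figure in the risk section. The grid makes matters worse: until the number of draws and the pre-dose volume are settled, no firm corrected total can be given, and staff working from the grid would take different samples from staff working from the flowsheet.

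**Working it through.** **Inputs**

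- Draws per sampling visit: 1 baseline + 6 timed = 7 (Section 4).
- Volume per draw: 41 ml (Section 4). The flowsheet agrees: 40 + 1 = 41 ml.
- Waste: 25 ml, included in the stated total (Section 4).
- Visits with this sampling: 2, Visits 1 and 4 (Section 4). Blood at Visits 2 and 3: none.
- Stated limit: less than 1½ cups (Section 10).
- Cup size: not given. Assumed range 236.6 ml (US cup) to 250 ml.

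**Step 1: reproduce the plan's figure.** 7 × 41 + 25 = 287 + 25 = 312 ml. This matches Section 4 exactly, so 312 ml is the total for one visit and not for two.

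**Step 2: whole study.** 2 × 312 = 624 ml.

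**Step 3: convert the limit.** 1.5 × 236.6 = 354.9 ml; 1.5 × 250 = 375 ml.

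**Step 4: compare.** One visit, 312 ml, is below the limit at either cup size. Two visits are not: 624 / 375 = 1.66 and 624 / 354.9 = 1.76. For 624 ml to stay below 1½ cups, a cup would have to exceed 624 / 1.5 = 416 ml.

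**Step 5: bounds from the conflicting schedules.** These combine entries from different places, so they show how far the total can move. They are not readings of any single schedule.

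| Reading | Per visit (ml) | Two visits (ml) | Multiple of limit |
|---|---|---|---|
| Lowest: 11 ml pre-dose (one 10 ml tube + 1 ml), six draws, no waste | 11 + 6 × 41 = 257 | 514 | 1.37 to 1.45 |
| Section 4 as written | 312 | 624 | 1.66 to 1.76 |
| With +15 min, 11 ml pre-dose, 25 ml waste | 11 + 7 × 41 + 25 = 323 | 646 | 1.72 to 1.82 |
| With +15 min, 41 ml pre-dose, 25 ml waste | 8 × 41 + 25 = 353 | 706 | 1.88 to 1.99 |

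The last two rows assume that waste stays at 25 ml per visit when a draw is added. Every row exceeds the limit over two visits.

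**The case against.** The best defence is that the sentence was meant per visit. One visit does take less than 1½ cups. The procedure list for Visits 1 and 4 still ends by declaring participation complete, which is not true at Visit 1. That suggests, though it does not prove, that single-visit wording was carried into a four-visit design. On this view a short qualifier would make the sentence accurate. The explanation is plausible, but it accounts for the error without removing it: the sentence as printed refers to being in the study, and a reader cannot infer the restriction.

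A second argument is that little follows from the cumulative figure. Section 4 gives the correct per-visit volume. The two sessions are about 12 weeks apart, while the protocol's own blood-donation exclusion looks back only 6 weeks. The listed risks, such as bruising and fainting, attach to each session. These points limit the seriousness and are fair. They do not make the stated figure right. The consent text was removed from the documents available, so what participants were told is unknown.

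Third, the grid mismatch is a separate defect, and the main conflict does not depend on it. That is correct. The pre-dose conflict also rests on a table extracted from PDF, where header placement is less certain than the explicit +15 row. The grid matters here because a corrected total depends on which draws are taken.

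Finally, it would be too strong to say that no analysis could be touched. The grid marks +15 min for NMR, and Section 14 compares enrichment over time with a mixed linear model. Keeping or dropping that sample would change the time points in that model. This point stands, and it is a consequence of settling the schedule, not of correcting the volume.

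**Conclusion.** The inconsistency is real. On the Section 4 schedule a participant who completes Visits 1 and 4 gives 624 ml, against a stated limit of 355 to 375 ml: an understatement by a factor of about 1.7 to 1.8. The only outside assumption is the cup size, and no plausible value rescues the sentence. Nor does the choice among the conflicting schedules, since the two-visit total runs from 514 to 706 ml.

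The sentence is true for a single visit on the Section 4 schedule. The error is one of disclosure and internal consistency. Correcting the volume alters no estimand, hypothesis test or sample size. It should be put right because it is a safety figure, the correct inputs are already in the protocol, and the correction is cheap.

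**What to change.** 1. Reconcile the sampling times and the pre-dose volume across Section 4, the flowsheet and the procedure grid, so that all three list the same draws. Which schedule applies is for the investigators to decide. If the +15 min sample is kept, add it to Section 4 and the flowsheet and recalculate the total, including the waste allowance.
2. Restate the volume in Section 10 both per visit and summed over Visits 1 and 4, in millilitres as well as cups. On the Section 4 schedule the figures are 312 ml and 624 ml.
3. Check that the participant information gives the same total.
4. Once the schedule is settled, state in Section 14 which sampling times enter the mixed linear model.

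The cost is a text amendment to Section 10 and the procedure grid, with Section 4 and the flowsheet also amended if the extra sample is kept, and a clarifying line in Section 14. The disclosed blood volume becomes less favourable.

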- The research materials that will be used for this proposal include demographic records and data (age, sex, weight, height, body mass index, abdominal MRI and dual x-ray absorptiometry imaging data currently collected and maintained in the Dallas Heart Study database), blood samples, and urine samples (females capable of pregnancy only). The blood and urine specimens will be taken at the time of study procedures and processed immediately. No samples will be stored. The database records that will be utilized include age, sex, race, cardiometabolic risk factor status, and data generated from blood tests and imaging phenotyping as part of the DHS study protocol.
- Prospective data to be obtained include current age, weight, height, waist circumference, hip circumference, calculated body fat percentage using both skinfold thickness at 7 different anatomical sites and bio-impedance analysis, a brief medical history, blood samples, and a urine pregnancy test (females only).
- For Aim 2, the FDA-approved drug, empagliflozin 10 mg by mouth daily, will be administered to those participants randomized to drug treatment. A matching placebo will be administered to participants not randomized to empagliflozin treatment. Both active drug and placebo will be obtained from the manufacturer (Boehringer-Ingelheim).
- No member of the study team will have access to individually identifiable private information about human subjects in the DHS. The DHS study coordinators have access to this information but are not part of the study team.
- Every study participant was assigned a randomly generated subject ID that is not linked to identifiable information. All data generated from a study participant is labeled with only their unique subject ID, including blood specimens and database records. The database records are kept on password protected servers in the DHS research center and managed by the study coordinators and statistical team. Investigators must have approved and authorized proposal to gain access to these data and all data transfers are managed by the database and statistical core. All analyses for this project will be conducted on site by the DHS statistical core. Measurements made during this study will be linked to participants in the database by the subject ID and merged into the database by the DHS statistical core.

9. Recruitment Methods and Consenting Process:

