The subject's experience during this procedure is identical to what they would experience during a clinical MRI (magnetic resonance imaging). MRI involves the use of a magnet and radio frequency energy. Therefore, patients who have implanted metal devices, such as pacemakers, certain aneurysm clips, or metal in the eye will be excluded. If subjects have any potential for metal in the body, the technologist or investigators should be informed before entering the magnet room. Because of the strong magnetic field associated with the scanner, it is rare, but possible, that a metallic object could fly through the air toward the scanner and hit the subject. To reduce this risk, everyone near the magnet will remove all metal from his or her clothing or pockets when in the scanning environment. There are no known risks or adverse effects resulting directly from exposure to magnetic fields and radio frequency energy used in this study. Some people feel claustrophobic in the MR scanner. If the subject is unable to tolerate being in the scanner, the scan can be stopped at any time. In addition, the MR scanner produces tapping sounds during operation, which may reach very loud levels. To minimize any discomfort from this noise, the subject will be provided with disposable earplugs and/or headphones that suppress external noise levels but do not eliminate voice communication with the scanner operator. In some cases, it is possible that the subject might experience neurostimulation effects, such as muscle twitches and tingling sensations, due to the rapid switching of magnetic field gradients used in these examinations. There are no known risks associated with these effects.

All subjects will be carefully evaluated by trained personnel prior to entering the MR scanner to exclude metal objects in or on their body. Any female of childbearing age will be screened and subjected to a pregnancy test, if indicated, prior to any MR procedure.

The MR scans in this study are designed for research, not for medical purposes. They are not useful for finding problems or diseases. In the event that a researcher discovers a possible abnormality, the subject will be informed. The subject will then consult with their primary care physician to discuss further tests and/or follow-up and treatment.

- *Risks to an Embryo, Fetus or Breast-fed Infant*

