Females: If females are part of this study while pregnant or breast-feeding an infant, it is possible that they may expose the unborn child or infant to risks. For that reason, pregnant and breast-feeding females cannot participate in the study. If participants can become pregnant, a pregnancy test will be done from a urine sample, and it must be negative before they can be a part of this study. If they do become pregnant during this study, they must tell the researchers immediately, and they will be removed from the study.

- *Loss of Confidentiality*

There is a potential risk of loss of confidentiality any time information is collected. Every effort will be made to keep participant information confidential; however, this cannot be guaranteed.

- *Other Risks*

There may be other side effects that are unknown at this time. If participants are concerned about other, unknown side effects, they will discuss this with the researchers.

11. Subject Safety and Data Monitoring:

Type of Research Data or Events to be Monitored:

All research activities described in the project summary will be monitored in addition to study data accrual, protocol deviations, protocol violations, unanticipated problems, and adverse events.

Methods and Frequency of Analysis:

All research staff will have appropriate training to ensure the safety of participants, the appropriate conduct of research, and the integrity of safety and/or efficacy of data. This training includes completion of all University-required training in the policies and procedures to protect the rights and welfare of people who participate in research.

Subjects will be fully informed about the study requirements throughout the conduct of the trial by the study personnel. At the beginning of the study, it will be noted in the research record that the subject received complete information about the study requirements. Study personnel will give participants information relevant to continued participation.

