14. Biostatistics – Statistical Analysis Plan:

Aim 1 Sample size calculation: Assuming 20% $^{13}\text{C}_3$ enrichment in subjects with low VAT (based on prior work), and an expected enrichment of between 15-18% among those with high VAT (SD 2%), for Aim 1 we expect to require 20 subjects per group to achieve 87% power to detect a 2% difference between groups at an alpha level of 0.05. Because we expect some patients may be deemed ineligible or withdraw consent in the interim between recruitment/informed consent is signed and undergoing study procedures, we will recruit up to a total of 50 subjects in order to ensure that 40 total subjects complete the study procedures (see sample size table). The study will be stopped after 40 subjects complete all study procedures and no further patients will be included in the study.

Variable	Mean Difference	Standard Deviation	Type 1 error (α)	Power ($1-\beta$)	Total N
----------	-----------------	--------------------	---------------------------	---------------------	---------

[U- ¹³ C ₃] glycerol enrichment	2%	2%	0.05	0.87	40
	3%	2%	0.05	0.89	20
	5%	2%	0.05	0.97	12
	7%	2%	0.05	0.89	6

Aim 1 Statistical analysis: Data will be expressed as means ± standard deviations. The primary outcome of mean [U-¹³C₃] enrichment of blood glucose at study end will be compared between high VAT and low VAT groups using the Student's t-test. Plots of [U-¹³C₃] enrichment over time for each group will be constructed to compare the trajectory of glycerol enrichment over time between groups and compared using a mixed linear model. The association between VAT and change in plasma blood glucose with glycerol challenge will be analyzed within each subject using a paired t-test and between groups by mean change in plasma glucose using the Student's t-test. The relationship between VAT and glycerol enrichment will also be modeled using linear regression and adjusted for potential confounders of age, ethnicity, family history of diabetes, triglycerides, lean mass, liver fat, abdominal subcutaneous fat mass, and biomarkers.

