Total Number of Tablets Dispensed at last visit: _____

Total Number of Tablets Returned Today: _____

Last Dose Kit #: _____ Last Dose Lot #: _____

COMPLIANCE % = $\frac{\text{TOTAL NUMBER OF TABLETS USED}}{\text{TOTAL NUMBER OF TABLETS REQUIRED PER PROTOCOL}} \times 100$
_____ / _____ X 100 = _____

Is Subject compliant with Medication? YES NO

If no, comment below and counsel/educate subject again:

If medication compliance percentage is <80%, please re-educate subjects. The subject can be withdrawn from study after 2 visits of medication noncompliance. The principal investigator should be notified for each subject's visit of not meeting medication compliance. It is up to the discretion of the principal investigator to allow the subject to remain in the study.

MEDICATION RE-DISPENSED YES NO

If no, comment below:

Kit #: _____ Lot#: _____ Expiration Date: _____

NUMBER OF TABLETS DISPENSED? _____

MEDICATION DOSAGE GIVEN TO AND REVIEWED WITH SUBJECT YES NO

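### No pregnancy test is scheduled between Visit 1 and Visit 4, so two monthly supplies of study drug are released on self-report alone

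*Combined protocol and SAP*

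**What the plan says.** Section 10 (Potential Risks, the paragraph on risks to an embryo, fetus or breast-fed infant) excludes pregnant and breast-feeding women because the child might be exposed to risk. It gives two protections. A woman who can become pregnant must have a negative urine test before joining. After that, "If they do become pregnant during this study, they must tell the researchers immediately, and they will be removed from the study".

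Section 4 (Study Procedures) lists the urine pregnancy test as step 4 of Visits 1 and 4. Visit 1 is baseline, and the flowsheet has drug supplied on Study Day 1. Visit 4 is the repeat visit after 3 months of drug; Section 3 gives the treatment period as 12 weeks.

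Visits 2 and 3 have five steps: arrival, pill-bottle return with adherence review, a safety enquiry ("Assess for any interval adverse effects and document as necessary"), dispensing of the next month's drug, and discharge. No urine test is listed, and no blood is drawn. The medication compliance form for these visits has the line "MEDICATION RE-DISPENSED YES NO" but no line for pregnancy status.

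Section 10 (MRI) adds a conditional test: "Any female of childbearing age will be screened and subjected to a pregnancy test, if indicated, prior to any MR procedure". MRI appears only among the Visit 1 and Visit 4 procedures.

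**The concern.** The removal rule works only if someone knows about the pregnancy. Self-report cannot catch a pregnancy the woman has not recognised, and the safety enquiry at Visits 2 and 3 has the same limit because it depends on what she says. The only later scheduled test, at Visit 4, comes when the drug course is over, so it can document an exposure but cannot shorten it.

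Visits 2 and 3 are therefore the two points at which a scheduled test could stop further supply, and neither has one. A pregnancy that begins early in treatment could be followed by up to two more monthly supplies. The eligible age range is 30–65, so women able to conceive can enrol. They are non-diabetic volunteers, and Section 13 does not guarantee them any direct benefit.

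**Working it through.** The plan states no figure on this point, so there is none to reproduce. The check has three parts.

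**1. Schedule count (from the documents)**

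| Visit | Approximate week | Urine test listed | Drug dispensed |
|---|---|---|---|
| 1 | 0 | yes | yes |
| 2 | 4 | no | yes |
| 3 | 8 | no | yes |
| 4 | 12 | yes | no (course complete) |

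Weeks 4 and 8 are inferred from monthly dispensing over 12 weeks. Dispensings without a scheduled test: 2 of 3. Longest gap between scheduled tests: about 12 weeks as written, about 4 weeks if Visits 2 and 3 are added. The pre-MRI test does not fill the gap, because no MRI is listed at Visits 2 or 3.

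**2. Length of exposure (model)**

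Assumptions: conception is uniform over weeks 0–12; a test is positive only if taken at least L weeks after conception, with L = 0 to 2 (not in the documents); drug stops at the first positive scheduled test or at week 12; and nobody recognises or reports a pregnancy. The last assumption makes these upper bounds.

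As written, exposure is 12 − c for conception at week c. Mean = 12/2 = 6.0 weeks; maximum 12.

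With tests at weeks 4 and 8, conceptions fall into three windows according to whether they are caught at week 4, caught at week 8, or run to week 12. The windows have lengths 4 − L, 4 and 4 + L. Exposure within each runs down linearly, with these window means:

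- L = 0: (4×2 + 4×2 + 4×2)/12 = 2.0 weeks; maximum 4.
- L = 1: (3×2.5 + 4×3 + 5×2.5)/12 = 2.67 weeks; maximum 5.
- L = 2: (2×3 + 4×4 + 6×3)/12 = 3.33 weeks; maximum 6.

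Mean saving: 6.0 − 3.33 = 2.7 weeks to 6.0 − 2.0 = 4.0 weeks. The third window gains nothing: 4/12 = 33% of conceptions at L = 0, and 6/12 = 50% at L = 2.

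If self-report does work, and each pregnancy is reported R weeks after conception (R is also an assumption), the same model gives:

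| R (weeks) | Mean exposure as written | Mean saving from the two tests (L = 2 to L = 0) |
|---|---|---|
| 6 | 4.5 | 1.2 to 2.5 |
| 4 | 3.3 | 0.3 to 1.3 |
| 3 | 2.6 | 0.1 to 0.8 |

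The model starts conception at Visit 1. A pregnancy begun just before Visit 1 could also test negative there if L is above zero. As written, no scheduled test would find it during the 12 weeks; with the change, the week-4 test would.

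**3. How many women**

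Section 14 says "we will recruit up to a total of 50 subjects in order to ensure that 40 total subjects complete the study procedures", and about half receive placebo. Assume 25–50% are women able to conceive and 1–5% of them conceive per year; neither figure is in the documents. With 12/52 = 0.231 of a year on drug:

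expected exposed pregnancies = N × share × 1/2 × annual rate × 0.231

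- Low: 40 × 0.25 × 0.5 × 0.01 × 0.231 = 0.012 (5 women on empagliflozin).
- High: 50 × 0.50 × 0.5 × 0.05 × 0.231 = 0.144 (about 12 women on empagliflozin).
- High share and rate with 40 participants: 40 × 0.50 × 0.5 × 0.05 × 0.231 = 0.115 (10 women on empagliflozin).

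**The case against.** The strongest reply is that nothing in the plan is broken. It promises an entry test and a reporting duty and delivers both; no section commits to monthly testing, and no analysis is affected. That is correct, and the point is put as a design choice.

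Second, the documents do not show that a few weeks less exposure matters. The adverse effects of empagliflozin listed in Section 10 include nothing fetal, and the embryo paragraph speaks only of possible risk. This stands as a limit on the claimed benefit. The plan nevertheless treats that possible risk as sufficient ground to exclude and to remove, and a removal rule is worth little without a means of detection.

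Third, the 12-week and 6.0-week figures suppose that the reporting duty never works. With prompt reporting the mean saving falls to between 0.1 and 2.5 weeks. This also stands, and the larger figures should be read as upper bounds only. Testing does not reduce the number of exposed pregnancies either; it shortens some of them. Over the whole trial the upper-bound saving is 0.012 × 2.7 = 0.03 to 0.144 × 4.0 = 0.6 woman-weeks.

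Fourth, the high count treats all 50 recruits as dosed, whereas Section 14 says the extra recruits cover people who drop out before study procedures. With 40 the upper figure is 0.115. The conclusion is the same.

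Finally, the consent pages are not in the available text and may contain contraception instructions, and Section 11 describes day-to-day monitoring of participants. Contraception advice would lower the conception rate, and staff contact gives occasions for disclosure. Neither detects an unrecognised pregnancy before the next bottle is handed over.

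**Conclusion.** The concern holds as an optional safety improvement. The schedule facts are certain: no scheduled pregnancy test between Visit 1 and Visit 4, two of three dispensings untested, and detection during treatment left to self-report.

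The benefit is less certain and small in expectation. It rests on the assumed test lag, share of women able to conceive, conception rate and speed of recognition. For an individual woman whose pregnancy goes unrecognised, the longest exposure before a scheduled test or the end of drug falls from 12 weeks to 4–6. For the trial as a whole, well under one exposed pregnancy is expected. The case for acting is that the cost is also very small. The endpoint, sample size and planned analyses are untouched.

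**What to change.** In Section 4, add the existing urine pregnancy test to the Visit 2 and Visit 3 steps, for females capable of pregnancy, immediately before drug is dispensed. Add one result line to the Visit 2/3 medication form beside the re-dispensing line. If the test is positive, withhold the drug and apply the removal rule already in Section 10. Test women in both arms so that blinding is unaffected.

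Cost: two strips per eligible woman. With 40 × 0.25 = 10 to 50 × 0.50 = 25 such women across both arms, that is 20–50 strips (at most 40 if only 40 participants are dosed). Add a few minutes at visits that already last 30–60 minutes, one form line and a protocol amendment. No blood draw is needed.
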